Treatment adherence in type 1 diabetes (T1D) tends to decline among adolescents, increasing risks of acute and chronic complications, excess health care use, poorer quality of life, and T1D-related family conflict. Poor adherence is associated with psychiatric and family dysfunction and often persists into early adulthood. Therapeutic advances such as continuous subcutaneous insulin infusion (CSII or "insulin pump") and continuous glucose monitoring (CGM) could improve metabolic control and quality of life. But, teens often do not benefit fully from such advances. Many studies of adults show that patient-centered communication styles predict more favorable clinical outcomes. Shared medical decision making (SMDM) interventions have improved outcomes among adults with diabetes and other conditions. Research in pediatrics has also shown that patient-centered and family-centered communication styles predict favorable outcomes, but most of this research is in primary care and has not studied youth with chronic conditions. Since there have been no controlled trials of SMDM with chronically ill youths, we propose a randomized controlled trial of an SMDM intervention compared with Usual Clinical Practice (UCP). Qualitative interviews of youths and parents who have previously faced these decisions and reliance on expert consultants, pediatric endocrinologists and diabetes educators have preceded this trial and provided valued input for refining the planned intervention and adapting the structured SMDM format for pediatrics. Now, we will recruit and randomize 166 11-<17 year old youth with T1D who are candidates for CSII or CGM (and a parent/caregiver) at all Nemours sites. The SMDM intervention will be delivered via a web-based platform, facilitated by Diabetes Educators (DEs) at each site in a standardized, yet individually tailored format. SMDM will employ multimedia "decision aids" prepared with the award-winning Nemours Center for Children's Health Media and the "e-city interactive" web design firm in Philadelphia in accord with pertinent international standards. SMDM will also include individualized assistance from the DE in assuring that each youth's and parent's preferences, values and cultural beliefs are carefully addressed and communicated to the attending endocrinologist. After a baseline evaluation and randomization to SMDM or UCP, effects on the primary outcome (treatment adherence; device utilization) and secondary outcomes (glycemic control, treatment alliance, decision conflict and regret, treatment satisfaction, diabetes-related distress and self-efficacy) will be measured over 1 year. Mixed effects modeling will be the primary analytic technique for evaluating effects on primary/secondary outcomes, examining selected variables as moderators and mediators of treatment effects, and assessing whether such effects are comparable for the two medical decisions of interest. The results will verify whether SMDM in this context enhances treatment adherence, device use and parent/patient-reported outcomes in youth with T1D.

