B2. Study Design The study design is a 2X5 randomized treatments design with 2 groups (SMDM and UCP) and 5 measurements (5 study visits at roughly 0, 3, 6, 9, and 12 Months). A diagram of the proposed RCT design appears below. (Checklists for the tasks to be completed at each visit can be found on the shared drive at S:\PCOR\grant\Coordinator Forms; access is limited to authorized members of the research team.) A 12 month follow-up was chosen over a longer follow-up period because the planned SMDM intervention is designed to facilitate more deliberate, systematic and collaborative decision making about the adoption of T1D treatment advances, based on the presumption that successful incorporation of these treatment advances over the first year of use will facilitate continued success thereafter. Facilitating better decisions is expected to lead to more effective utilization of the available treatment option among those who accept it and prevention of unsuccessful attempts at utilizing that treatment option among those who reject it. Based on our prior trials of the adoption of intensified therapy and of continuous glucose monitoring, success or failure of that endeavor will be readily apparent for the vast majority of adolescents within 12 months and very few who initially fail to benefit will do so later.^{10-13, 15-17, 19-20} A longer study could inhibit recruitment, would be more expensive and cumbersome, would not be feasible with this funding mechanism, would delay dissemination of the findings and would not add appreciably to the scientific merit. As noted above, unless PCORI allows a no-cost extension, follow-up for later-enrolling participants may be truncated at 6 months since the project currently must end by 3/31/16 and time must be allowed at the end of the project for data management and analysis.

DIAGRAM OF RCT STUDY DESIGN

REPEAT EVALUATIONS

- Measures of decision quality and CSII or CGM use
- HbA1c; Hypoglycemia Diary;
- Questionnaires at appropriate intervals until 12 months after Baseline

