SMDM by definition seeks to reflect the perspectives of youths, parents, and HCPs and that is how the proposed intervention has been designed. The visits with the Diabetes Educator (DE) and use of the decision aids are designed to equip parents and youth to have more meaningful and productive discussions with HCPs about the merits of the treatment option of interest than they might achieve without the SMDM intervention. This enhanced communication, along with personal ownership of the decision, is expected to help adolescents and parents make an important treatment decision more effectively with their HCP. Hence, each SMDM patient will collaborate with their diabetes HCP and DE to reach an informed decision about CSII or CGM. We will document details of each participant's educational experiences during the decision making process as a means of verifying the integrity of the experimental manipulation (See Appendix). Each parent/adolescent dyad randomized to SMDM will have an initial orientation visit with a trained research staff member (either in person or via a scheduled phone conference), consisting of an introduction to SMDM and to the structure, content and operation of the decision aid to be used by that family. The parent and adolescent will be asked to use the decision aid over the subsequent 2-4 weeks and to come prepared to discuss with the DE at the second visit each of the discussion points that appear throughout the decision aid, as well as any other questions or comments they might wish to address. At the second visit, the DE will prepare a summary of the family's SMDM experience that will be sent to the adolescent's T1D HCP for discussion at their next clinic visit and to the research team as a process measure of each family's SMDM experience. Each HCP will be provided with a brief orientation regarding the structure of the SMDM intervention and they will be invited to inspect/use each of the two decision aids at their convenience.

UCP Intervention: The UCP intervention will consist of the education and consultation procedures currently employed at each of the participating sites for patients and families who are considered by the health care team to be suitable candidates for either CSII or CGM. There is some variability across sites and physicians in

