Insulin Pump and Continuous Glucose Monitor Downloads: Device downloads will be the primary outcome measures since these measures will reflect the extent to which participants demonstrate optimal use of CSII or CGM. At Visits 2 through 5, staff will download insulin pumps and CGM devices for those using them, or adolescents can e-mail data download files to the research team prior to each of those visits. For insulin pump users, the number of bolus infusions, number of times the "bolus wizard" was used and percentage of days on which fewer than 3 bolus infusions of insulin were registered will be recorded. For CGM users, the mean number of hours per day of stored CGM data will be captured from device downloads. Complete cessation of the chosen treatment will also be recorded if it occurs, which is expected to be much more common among adopters of CGM compared with adopters of CSII. Each of these scores will be transformed into z-scores relative to the full sample, permitting combined treatment of these measures in the planned analyses. Another analytic option would be to utilize an operational criterion to dichotomize patients into "Optimal" or "Suboptimal" users of CSII or CGM for the purpose of testing logistic regression models of SMDM effects. This determination will be made by [name], the project statistician.

Measures obtained at the first post-decision visit only

These measures will be obtained at the next study visit for those participants who have reached a decision. The Measurement schedule depicts this as Visit 2, which is expected to be the case for most participants, but some participants may take longer to reach a decision.

SMDM Satisfaction Scale: This measure, constructed for this study, will be completed only by adolescents and parents at the next study visit following their actual receipt and initialization of the chosen device (CGM or insulin pump). This scale is to be completed only by SMDM participants.

SMDM Satisfaction Scale- Clinician Form: This measure will be completed by clinicians at the first visit after each parent and adolescent in the SMDM group have reached a decision about the technology of interest (pump or CGM) to assess their level of satisfaction with how helpful the decision aid was for the patient/parent in the decision making process. The measure includes 5 items rated on a 5 point scale and space for the clinician to write additional comments. This will be completed for patients in the SMDM group only.

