Description of Decision Making Process: This 10-item measure asks parents and adolescents in the UC Group only to report how often they did certain activities during the decision making process and how it affected their choice, the outcome of the decision making process and how satisfied they are with their decision. This measure was constructed for this study to enable participants randomized to the UCP group to describe the process by which they made a decision about CSII or CGM. If decision making has been actively deferred, that will be treated as a decision having been made. If decision making has simply not occurred, in the absence of a definite statement to defer decision making until some point in the future, this measure will be obtained at Visits 3 and 5. Information yielded from this measure will be used primarily for descriptive purposes to enable readers to place the UCP condition in a concrete perspective.

Measures obtained at Visit 3 and Visit 5

Decision Regret Scale (DRS): The DRS is a 5-item scale for measuring a patient's degree of regret (or satisfaction) after a specific decision.¹⁶³ Items are rated on a 5-point scale ranging from "strongly agree" to "strongly disagree", and higher scores reflect more perceived regret. Internal consistency was .81 in a prior study. The scale will be completed by parents and adolescents in both the SMDM and UCP groups. Administration time is about 2-3 minutes.

SURE Test: The SURE Test is a 4-item screening tool to measure decisional conflict in patients facing clinical decisions in primary care. If the total score is less than 4, the patient is experiencing decisional conflict. The SURE Test will be completed by parents and youth in both groups at Visit 3 and at Visit 5. Administration time is about 2-3 minutes.

Measure obtained at Baseline (Visit 1) and Visit 2

Test of CSII or CGM Knowledge: Each parent and adolescent will complete a 5-item test of CSII or CGM knowledge based on content of the respective decision aids at baseline and at Visit 2 (Or the first visit after the

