Insulin Pump Use Profile/CGM Use Profile (P,C)					
Hypoglycemia Diary (B)					

HbA _{1c} (A)					
Rapid Estimate of Adult/Adolescent Literacy in Med. (B)					
Diabetes Numeracy Test (B)					
Diabetes Self Management Profile-Self Report (B)					
Test of CSII or CGM Knowledge (B)					
Decision Regret Scale (B)					
SURE Test (B)					
Diabetes Technology Questionnaire (B)					
SMDM Satisfaction Scale (B, HCP)					
Description of Decision Making Process (B)					
Decision Aid Utilization Statistics (Monthly Reports)					

*Baseline assessment (0 Months) will occur just prior to randomization to SMDM or UCP. Respondents for each measure are HCP =Adolescent's diabetes health care provider; P = Parent; A= Adolescent; B = Both. All measures are obtained from both the SMDM and UCP groups unless otherwise stated. The Decision Regret Scale, SURE Test and the Description of the Decision Making Process may be repeated at other visits if additional medical decisions (CSII, CGM) are raised for consideration. The Test of CSII or CGM Knowledge will be administered at the first post-decision visit, which is expected to be Visit 2 for most participants. As mentioned above, those who enroll after 3/31/15 are likely to be followed for only 6 months unless PCORI

decides to allow no-cost extensions.

B.5. Statistical Analyses:

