Data Management and Statistical Analysis Plans The primary efficacy endpoints are indices of extent of engagement in CSII (mean number of bolus infusions/day; mean number of uses of "wizard" functions/day) or CGM use (mean number of hours of CGM use/day); and measures of decision quality (Test of CSII or CGM Knowledge; SURE Test; Decision Regret Scale; Diabetes Technology Questionnaire) at each post-decision visit. Secondary efficacy endpoints will include: HbA_{1c} measured quarterly, treatment adherence (DSMP-SR parent and youth) total scores obtained at Visits 1, 3 and 5; and Hypoglycemia Diary obtained at each quarterly clinic visit.

The Full Analysis Set will consist of all participants who provided at least one post baseline assessment record. The Completer Analysis set will include all participants who provided all post baseline primary efficacy assessment results.¹⁶⁶⁻¹¹⁶⁸ Efficacy analyses will be performed on both sets, providing both "Intention to Treat" (Full Analysis Set) and "Per-Protocol" (Completer Analysis Set) analyses. All collected data will be summarized in graphs and tables. Categorical variables will be summarized using frequencies and percentages, while quantitative variables will be described by presenting mean, median, standard deviation (or standard error of mean), minimum and maximum. Data will be summarized by group (SMDM and UCP) and type of medical decision (CSII or CGM) as well as assessment time points. Besides tabular presentation, graphical presentations of some important variables related to primary and secondary endpoints will be provided.

Assumptions for all proposed models will be checked before statistical analyses.¹⁶⁶⁻¹⁶⁸ Appropriate transformations or non-parametric methods will be used in cases of violated model assumptions. For graphical comparison of data that are sufficiently normally distributed, group means and SE of mean will be presented via bar charts. In case of substantial deviation from normality, side by side boxplots will be used for graphical comparisons. Exploratory Subgroup analyses will be conducted as needed. All tests will be performed against a two-sided alternative at the $\alpha = 0.05$ significance level and a 95% confidence interval and/or a p-value will be provided for inferential purposes. Data from all clinics will be pooled for the analyses. All analyses will be performed using the most recent version of the SAS statistical software package.

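### The analysis plan wants SURE at every visit after the decision, but SURE is first given at Visit 3, about three months after most families are expected to have decided

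*Combined protocol and SAP*

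**What the plan says.** Section B.5 names as primary efficacy endpoints the indices of device use and "measures of decision quality (Test of CSII or CGM Knowledge; SURE Test; Decision Regret Scale; Diabetes Technology Questionnaire) at each post-decision visit". In the same section, Hypothesis 1 predicts an SMDM advantage on these measures at every follow-up assessment, and Hypothesis 3 makes SURE one of the mediators of the effect on device use and satisfaction.

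Section B.3 describes the instrument: "The SURE Test is a 4-item screening tool to measure decisional conflict in patients facing clinical decisions in primary care". It sets the timing: "The SURE Test will be completed by parents and youth in both groups at Visit 3 and at Visit 5". The B.4 schedule marks the same two visits, with no SURE at baseline or Visit 2. The B.4 footnote adds one exception: "The Decision Regret Scale, SURE Test and the Description of the Decision Making Process may be repeated at other visits if additional medical decisions" come up. That covers a further decision, not the one for which the family enrolled.

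On the calendar, B.2 gives "5 measurements (5 study visits at roughly 0, 3, 6, 9, and 12 Months". For measures tied to the first visit after the decision, B.3 says: "The Measurement schedule depicts this as Visit 2, which is expected to be the case for most participants". The Knowledge Test uses that slot. On the intervention, B.2 says: "The parent and adolescent will be asked to use the decision aid over the subsequent 2-4 weeks". A session with the diabetes educator and a clinic visit with the health care provider (HCP) then close it.

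The Abstract assigns a different status, placing conflict among the "secondary outcomes (glycemic control, treatment alliance, decision conflict and regret, treatment satisfaction, diabetes-related distress and self-efficacy".

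**The concern.** SMDM is a short intervention aimed at the moment of choice, and B.2 says it is meant to improve decision quality rather than adherence in general. Decisional conflict is the measure most directly tied to that moment, yet the plan takes no reading of it near the time when most families are expected to choose.

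Two things are at stake. First, the endpoint definition and the schedule do not match, so the primary analysis of SURE cannot be carried out as B.5 words it. Second, Hypothesis 3 needs a mediator that is measured before, or at least alongside, the outcome it is said to explain. A first SURE reading at Visit 3 follows the first scheduled recording of device use. Conflict at the time of the decision cannot be recovered afterwards.

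**Working it through.** The plan states no figure for this interval. The check uses the nominal calendar and a comparison of the schedules.

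**Inputs**
- Visits 1 to 5 fall at about 0, 3, 6, 9 and 12 months (B.2, B.4).
- SURE is given at Visits 3 and 5 (B.3, B.4).
- The first visit after the decision is expected to be Visit 2 for most families (B.3, B.4 footnote).
- The decision aid is used for 2 to 4 weeks after orientation (B.2).
- Device downloads take place at Visits 2, 3, 4 and 5 for those who have the device (B.3).

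**Gap from decision to first SURE**
- Visit 3 − Visit 2 = 6 − 3 = 3 months. A family that has decided by Visit 2 therefore has its first SURE at least about 3 months after the decision.
- The second reading is Visit 5 − Visit 2 = 12 − 3 = 9 months or more after it.

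**Gap from end of decision-aid use to first SURE** (assuming orientation at about month 0 and 4.345 weeks per month)
- Two weeks of use: 2 / 4.345 = 0.46 months, and 6 − 0.46 = 5.5 months.
- Four weeks of use: 4 / 4.345 = 0.92 months, and 6 − 0.92 = 5.1 months.

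**Mediator against outcome.** B.5 says mediators will be measures collected serially and alongside the primary endpoints. Downloads are scheduled at four visits and SURE at two of them (3 and 5). The earliest download visit has no SURE. Hypothesis 3 also speaks of changes in decision quality. Without a baseline SURE, the only change available is from Visit 3 to Visit 5.

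**Index decision against a second decision.** For an adolescent who later adds the other device, the practical-considerations table in B.2 collects decision-quality measures at the next study visit once that device is in use. The index decision has no comparably prompt SURE reading.

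**Shortened follow-up.** B.1 foresees 6 months of follow-up for late enrollers unless an extension is granted. Those families would have one SURE reading only, at Visit 3.

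**The case against.** The strongest reply is that later measurement is deliberate and that the decision window is wide. B.2 looks for lasting success over the first year. B.3 places the questionnaire load on Visits 1, 3 and 5, which carry the gift card, and keeps Visit 2 light. Under usual practice B.2 describes decisions as spread over several visits, and it plans for indecision, deferral and insurance delays. Some families, plausibly more in UCP, may still be deciding at Visit 3. This stands: the three-month gap applies to families who decide by Visit 2, and the interval from decision to SURE may differ by arm. A reader should not infer that both arms are affected alike.

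The wording in B.5 may also be loose. It cannot be literal for the Knowledge Test, which is given once after the decision. That weakens the mismatch as evidence that a Visit 2 SURE was intended. It does not supply a reading near the decision.

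A reader might go further and infer that the effect will have faded by Visit 3, so that a real benefit would be missed. The documents do not support that. They say nothing on how SURE changes between months 3 and 6. They give neither a standard deviation nor a proportion for this four-item screen with a cut-off, so no loss of power can be calculated. Nor do they show that SURE at Visit 3 merely repeats the Decision Regret Scale. B.3 describes two different constructs, and sharing visits does not make them redundant.

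**Conclusion.** The concern holds as a mismatch between endpoint and schedule, and as a gap in timing. SURE is a primary measure in B.5, to be assessed at every visit after the decision. Under B.3 and B.4 it is absent from the visit that the plan itself expects to be the first such visit for most families.

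For those families the delay is at least about 3 months from the decision. It is about 5.1 to 5.5 months from the end of decision-aid use if orientation falls near month 0. Both figures rest on the nominal visit months, and actual clinic visits will vary.

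The consequences are that decisional conflict near the choice goes unmeasured for most families, and that SURE is a weaker mediator in Hypothesis 3. Whether the SMDM effect on SURE is smaller at Visit 3 than at Visit 2 is unknown.

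Endpoint status also needs reconciling. The Abstract makes decision conflict secondary, and B.3 calls device downloads the primary outcome measures. Aim 3, B.2 and B.5 treat decision quality as primary. The timing problem remains under either label.

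**What to change.** - Give SURE at Visit 2 to all randomized parents and youths, whether or not they have decided, and record at that visit whether a decision has been reached. Allow online completion: B.3 reserves in-person completion for the knowledge, literacy and numeracy tests, and families recruited remotely under Plan C need not attend clinic.
- Where the first visit after the decision is later than Visit 2, make sure SURE is given then. Visits 3 and 5 already have it, so this adds a form only when that visit is Visit 4.
- Keep Visits 3 and 5, and enter all time points in the planned mixed model. Report decision status descriptively. It arises after randomization, so comparing arms within decided or undecided families is not a randomized comparison. The same caution applies to Visit 4 readings, which would come from late deciders only.
- Align B.3 and B.4 with B.5 and Hypothesis 1, and settle whether decision conflict is primary or secondary.

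Visit 2 need not become the lead time point. SMDM families may have just finished structured counselling while UCP families are still mid-process, so a Visit 2 difference would partly reflect stage of decision.

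**Cost.** B.3 puts SURE at two to three minutes. Two administrations take 4 to 6 minutes per respondent over the study, and three take 6 to 9. A schedule amendment is needed, and Visit 2 becomes slightly less light. A Visit 2 reading still provides no baseline, so the changes in Hypothesis 3 would run from Visit 2 onward.
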